7.2. Laboratory Evaluations

Laboratory collected during the study will be analyzed and summarized using both quantitative and qualitative methods. Summaries of laboratory data will be provided for the Safety Analysis Set and will include data collected up to the last dose of filgotinib plus 30 days for subjects who have permanently discontinued filgotinib in GLPG0634-CL-205, or all available data at the time of the database snapshot for subjects who were ongoing at the time of an interim analysis. The analysis will be based on values reported in conventional units. When values are below the LOQ, they will be listed as such, and the closest imputed value will be used for the purpose of calculating summary statistics as specified in Section 3.4.

A by-subject listing for laboratory test results will be provided by subject ID number and visit in chronological order for hematology, serum chemistry, and urinalysis separately. Values falling outside of the relevant reference range and/or having a severity grade of 1 or higher on the CTCAE severity grade will be flagged in the data listings, as appropriate.

No formal statistical testing is planned.

7.2.1. Summaries of Numeric Laboratory Results

Descriptive statistics of filgotinib baseline values, values at each postbaseline visit and change from filgotinib baseline at each post baseline visit will be provided by treatment group for the following laboratory tests:

- Hematology
 - Hematocrit
 - Hemoglobin
 - Platelet count
 - Red blood cell count
 - White blood cell (WBC) count

- Lymphocytes
- Monocytes
- Neutrophils
- Eosinophils
- Basophils
- Chemistry
 - Alanine aminotransferase (ALT)
 - Aspartate aminotransferase (AST)
 - Alkaline phosphatase (ALP)
 - Total bilirubin
 - Serum creatinine
 - Creatinine clearance by Cockcroft-Gault formula
 - Glucose
- Lipid
 - Triglycerides
 - Total cholesterol
 - HDL
 - LDL
 - LDL/HDL ratio
- Hormone in male subjects
 - Follicle stimulating hormone
 - Inhibin B
 - Luteinizing hormone
 - Testosterone

A filgotinib baseline laboratory value will be defined as the last measurement obtained on or prior to the date/time of first dose of filgotinib in the core studies or GLPG0634-CL-205. Change from filgotinib baseline to a postbaseline visit will be defined as the visit value minus the filgotinib baseline value. The mean, median, Q1, Q3, minimum, and maximum values will be displayed to the reported number of digits; SD values will be displayed to the reported number of digits plus 1.

Median (Q1, Q3) of the observed values for the laboratory tests specified above will be plotted using a line plot by treatment group and visit.

In the case of multiple values in an analysis window, data will be selected for analysis as described in Section 3.5.3.

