Up to Week 12, small increases were observed in mean hemoglobin concentrations in the filgotinib 200 mg daily dose groups (increase of 4.4 g/L from baseline in the filgotinib 100 mg bid group). Thereafter, hemoglobin mean concentrations appeared to plateau and remain stable until Week 24 (increase of 4.9 g/L from baseline in the filgotinib 100 mg bid group).

Up to Week 4, dose-dependent decreases were observed in mean absolute neutrophil counts in the filgotinib treatment groups. Mean absolute neutrophil counts appeared to plateau and remained stable until Week 24. No decreases in mean absolute lymphocyte counts were observed, including lymphocyte subsets.

Up to Week 4, dose-dependent decreases were observed in mean absolute platelet counts in the filgotinib treatment groups. Mean absolute platelet counts appeared to plateau and remained stable. Dose-dependent increases in the filgotinib groups were observed in mean creatinine concentrations during the first 4 weeks of the study for most filgotinib treatment groups (up to Week 8 for the filgotinib 100 mg bid group) that subsequently plateaued and remained stable up to Week 24.

Up to Week 4, dose-dependent increases were observed in mean concentrations of total cholesterol, LDL cholesterol, high-density lipoprotein (HDL) cholesterol, and triglycerides in all filgotinib treatment groups. All these lipid parameters further increased up to Week 8 in the filgotinib 200 mg daily dose groups. Thereafter, these increases appeared to plateau and maintained at stable mean concentrations up to Week 24. At Week 24, mean increases were observed of 0.7 mmol/L in total cholesterol, 0.3 mmol/L in LDL cholesterol, 0.3 mmol/L in HDL cholesterol, and 0.1 mmol/L in triglycerides in the filgotinib 100 mg bid group.

In male subjects, small non dose-dependent increases were observed in total and free testosterone during the study (at Week 24, mean increases were 3.4 nmol/L for total and 51.7 pmol/L for free testosterone in the filgotinib 100 mg bid group). For FSH, inhibin B, LH, and prolactin, small changes (both increases and decreases) were observed during the study, without any trends of larger changes in male subjects of one or more of the different treatment groups.

GLPG0634-CL-204, Filgotinib administered as monotherapy in RA Subjects

The primary objective of study GLPG0634-CL-204 was to evaluate the efficacy of three doses of filgotinib q.d. compared to placebo at Week 12.

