In case of temperature excursions (outside the permitted range mentioned above), the sponsor should immediately be contacted for evaluation of the excursion and further use of the study drug.

Until dispensed to the subjects, all drug products should be stored in a securely locked area, accessible only to authorized site personnel. To ensure the stability of the study drug and to ensure proper product identification, the drug product should not be stored in a container other than the container in which it is supplied.

Consideration should be given to handling, preparation, and disposal through measures that minimize drug contact with the body. Appropriate precautions should be followed to avoid direct eye contact or exposure when handling.

8.6.4 **Method of Assigning Subjects to Treatment Groups**

Following completion of one of the previous core studies (GLPG0634-CL-203 or GLPG0634-CL-204), subjects who are deemed by the investigator to benefit from continued therapy with study medication, will be offered the option to enter this Long-term Follow-up study. All subjects who opt to roll over into this study will be enrolled and will start the study at the same dose (filgotinib 200 mg daily, administered as either 200 mg q.d. or as 100 mg b.i.d., depending on the q.d./b.i.d. regimen of the preceding core study). Subjects who were on 24 weeks of placebo during the core study

GLPG0634-CL-203 will be randomly assigned to either 100 mg b.i.d. or 200 mg q.d. All other subjects will switch to 200 mg daily, keeping the same regimen (q.d. or b.i.d.) they had in the preceding core study.

This will be done according to a pre-specified randomization scheme prepared by an independent statistician within [REDACTED]. Upon qualification for the study, subjects will be randomized using a computerized interactive voice/web response system (IXRS) [REDACTED] to filgotinib 200 mg q.d. or 100 mg b.i.d. in a 1:1 ratio.

For each subject at each visit, the clinic will contact the IXRS system and will be given the appropriate kit number to be dispensed. The kit will contain the relevant study medication until the next visit.

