1.1. Study Objectives

The primary objective of this study is as follows:

- To evaluate the long term safety and tolerability of filgotinib for the treatment of rheumatoid arthritis (RA)

The secondary objectives of this study are as follows:

- To evaluate the long-term efficacy of filgotinib
- To evaluate the long-term effects of filgotinib administration on subjects' disability, fatigue, and quality of life

GLPG0634-CL-205 data and the most current GLPG0634-CL-203 and GLPG0634-CL-204 data will be used in the analyses.

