3.5. Analysis Visit Window

3.5.1. Definition of Study Day

The first dose date of individual study drug will be calculated separately for each study drug in a treatment group. Study Day 1 is defined as the first dose date of any study drug, which is the minimum of the first dose dates of individual study drugs in a treatment group.

The last dose date of individual study drug will be calculated separately for each study drug in a treatment group. The last dose date of any study drug will be defined as the maximum of the last dose dates of individual study drugs in a treatment group.

The first dose date of individual study drug in GLPG0634-CL-205 is identified by the first drug dispense date + 1 day. The last dose date of individual study drug in GLPG0634-CL-205 is identified by the Final Visit date or the Early Discontinuation Visit date.

Study Day will be calculated from the Reference Date and derived as follows:

- For postdose study days: Assessment date – Reference Date + 1
- For days prior to the first dose: Assessment date – Reference Date

Reference Date is defined as follows:

- For efficacy data in the core studies: Study Day 1 in the core studies
- For efficacy data in GLPG0634-CL-205: Study Day 1 in GLPG0634-CL-205
- For safety data: The first dose date of filgotinib in the core studies or GLPG0634-CL-205

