3.5.2. Analysis Visit Windows

Subject visits may not occur on protocol-specified days. Therefore, for the purpose of analysis, observations will be assigned to analysis windows for efficacy data in the core studies (Table 3-1 and Table 3-2) and GLPG0634-CL-205 (Table 3-3 and Table 3-4), and for non-efficacy data (Table 3-5). The analysis visit windows for non-efficacy data will be applied up to the last dose date of any study drug.

The baseline value is defined as follows:

Efficacy data:

- Core baseline: The last nonmissing value on or prior to the first dose date of study drug in the core studies
- Extension baseline: The last nonmissing value on or prior to the first dose date of study drug in GLPG0634-CL-205, and no earlier than the core study nominal Week 24 visit date

Safety data:

- Filgotinib baseline: The last nonmissing value on or prior to the first dose date of filgotinib in the core studies or GLPG0634-CL-205

Table 3-1. Analysis Visit Windows for Efficacy Data (SF-36 and FACIT-Fatigue Excluded) in the Core Studies

Analysis Visit	Nominal Study Day	Lower Limit	Upper Limit
Core Baseline	1	(none)	1
Core Week 1	8	2	11
Core Week 2	15	12	22
Core Week 4	29	23	43
Core Week 8	57	44	71
Core Week 12	85	72	99
Core Week 16	113	100	127
Core Week 20	141	128	155
Core Week 24	169	156	≥169

Table 3-2. Analysis Visit Windows for SF-36 and FACIT-Fatigue in the Core Studies

Analysis Visit	Nominal Study Day	Lower Limit	Upper Limit
Core Baseline	1	(none)	1
Core Week 4	29	2	57
Core Week 12	85	58	127
Core Week 24	169	128	≥169

Table 3-3. Analysis Visit Windows for Efficacy Data (SF-36 and FACIT-Fatigue Excluded) in GLPG0634-CL-205

Analysis Visit	Nominal Study Day	Lower Limit	Upper Limit
Extension Baseline	1	(none)	1
Extension Week 12	85	2	127
Extension Week 24	169	128	211
Extension Week 36	253	212	295
Extension Week 48	337	296	379
Extension Week 60	421	380	463
Extension Week 72	505	464	547
Extension Week 84	589	548	631
Extension Week W	7xW+1	7xW-40	7xW+43

Table 3-4. Analysis Visit Windows for SF-36 and FACIT-Fatigue in GLPG0634-CL-205

Analysis Visit	Nominal Study Day	Lower Limit	Upper Limit
Extension Baseline	1	(none)	1
Extension Week 48	337	2	505
Extension Week 96	673	506	841
Extension Week W	7xW+1	7xW-166	7xW+169

Table 3-5. Analysis Visit Windows for Non-Efficacy Data

Analysis Visit	Nominal Study Day	Lower Limit	Upper Limit
Filgotinib Baseline	1	(none)	1
Week 12	85	2	127
Week 24	169	128	211
Week 36	253	212	295
Week 48	337	296	379
Week 60	421	380	463

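### By-visit laboratory means pool core-study doses below 200 mg per day with later values at 200 mg, so for dose-dependent analytes the roll-over dose step cannot be told from a time effect over Weeks 12 to 36

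*SAP*

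**What the plan says.** SAP 1.1 brings the core data in: "GLPG0634-CL-205 data and the most current GLPG0634-CL-203 and GLPG0634-CL-204 data will be used in the analyses". SAP 3.5.1 sets the reference date: "For safety data: The first dose date of filgotinib in the core studies or GLPG0634-CL-205". SAP 3.5.2 gives laboratory data one baseline: "Filgotinib baseline: The last nonmissing value on or prior to the first dose date of filgotinib in the core studies or GLPG0634-CL-205". An extension baseline exists there too, but only for efficacy data. On this clock, SAP 7.2.1 tabulates by treatment group and visit: "Descriptive statistics of filgotinib baseline values, values at each postbaseline visit and change from filgotinib baseline at each post baseline visit will be provided".

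SAP 3.2 defines two groups: filgotinib with MTX (all subjects from CL-203) and filgotinib monotherapy (all subjects from CL-204). Neither is split by core-study dose.

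Core filgotinib doses were 50, 100 or 200 mg per day. Protocol 8.6.4 sends CL-203 subjects who had 24 weeks of placebo to 200 mg per day by randomisation between the two regimens, and adds: "All other subjects will switch to 200 mg daily, keeping the same regimen (q.d. or b.i.d.) they had in the preceding core study". SAP 1.2 notes one exception, US males, who were held at 100 mg q.d. Investigators may also reduce the dose.

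Protocol 6.4 reports for CL-203: "Up to Week 4, dose-dependent decreases were observed in mean absolute neutrophil counts in the filgotinib treatment groups". It describes platelets, creatinine and lipids as dose-dependent too, with changes that settle within about 4 to 8 weeks and then stay level.

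**The concern.** Long-term safety is the primary objective. Protocol 6.6 says the study looks for effects of long-term administration of a stable 200 mg daily dose, and Protocol 8.9.1.3 says the laboratory summaries are there to pick up changes attributable to dosing. A by-visit mean does that cleanly only if the dose is the same across the visits compared. Here the dose changes by design, and for most subjects who started filgotinib in a core study it changes between two adjacent visits.

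If an analyte responds to dose and plateaus quickly, its pooled mean will move when the subjects below 200 mg are stepped up, even if nothing changes with time on a fixed dose. A reader of the planned table could take that for a delayed drug effect. Equally, a real change at about that time could be put down to the dose step. The table holds nothing that separates the two.

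**Working it through.** The plan gives no figure for this point. Its only computed figure, the sample size, reproduces as 0.7 × (595 + 280) = 612.5 against the stated 612, and is not needed below.

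**Where the visits fall.** Under "Table 3-5. Analysis Visit Windows for Non-Efficacy Data", Week W covers days 7W − 40 to 7W + 43. Week 24 is therefore days 128–211 and Week 36 is days 212–295; Week 12 is days 2–127. Three kinds of subject follow:

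- Filgotinib from core Day 1: core Week 12 is day 85 (Week 12), core Week 24 is day 169 (Week 24), and the extension Week 12 visit is about day 169 + 85 = 254 (Week 36). The roll-over step lies between Weeks 24 and 36.
- Placebo, switched at core Week 12 (first filgotinib at about core day 86): core Week 24 becomes day 169 − 86 + 1 = 84 (Week 12, at 100 mg per day), and extension Week 12 becomes day 254 − 86 + 1 = 169 (Week 24, at 200 mg).
- CL-203 placebo for 24 weeks (first filgotinib at about core day 170): extension Week 12 is day 254 − 170 + 1 = 85 (Week 12, already at 200 mg). This is first exposure and not a step-up.

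**Dose mix.** Arm sizes come from Protocol Tables 6-1 and 6-2. Equal roll-over by arm is assumed: 739 of 877 (84%) rolled over and the split by arm is not given.

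- CL-203: 50 or 100 mg per day, 82 + 85 + 86 + 85 = 338; 200 mg per day, 86 + 84 = 170; placebo 86; total 594.
- CL-204: 50 or 100 mg per day, 72 + 70 = 142; 200 mg per day, 69; placebo 72; total 283.
- Randomised to filgotinib below 200 mg: (338 + 142) / (508 + 211) = 480/719 = 67%.

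Share of values at 200 mg per day, p:

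| Visit | CL-203 (with MTX) | CL-204 (monotherapy) |
|---|---|---|
| Week 12 | 33% to 39%* | 69/283 = 24% |
| Week 24 | (170 + 86)/594 = 256/594 = 43% | (69 + 72)/283 = 141/283 = 50% |
| Week 36 | near 100% by design | near 100% by design |

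*(170 + 86r)/594, with the share r of placebo subjects who respond and stay on placebo assumed between 30% and 70%.

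**Size, as an illustration.** The documents give no mean laboratory changes for the lower doses. Let f be the effect below 200 mg as a fraction of the effect at 200 mg, with no true drift. The pooled mean change at Week 24 is m = p + f(1 − p) of the full effect, it is 1 at Week 36, and the apparent further change is 1/m − 1.

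| f | CL-203: m | Further change | CL-204: m | Further change |
|---|---|---|---|---|
| 0.25 | 0.431 + 0.25 × 0.569 = 0.573 | 74% | 0.498 + 0.25 × 0.502 = 0.624 | 60% |
| 0.50 | 0.716 | 40% | 0.749 | 33% |
| 0.75 | 0.858 | 17% | 0.875 | 14% |

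On an absolute scale, Protocol 6.4 gives a 0.7 mmol/L rise in total cholesterol at Week 24 for 100 mg b.i.d. in CL-203. The step alone would then be 0.569 × (1 − f) × 0.7, or about 0.30 to 0.10 mmol/L for f from 0.25 to 0.75.

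**Where the step sits.** In units of (1 − f), the Week 12 to 24 part is 0.04 to 0.10 in CL-203 and 0.498 − 0.244 = 0.25 in CL-204. The Week 24 to 36 part is 0.57 and 0.50. The later interval carries most of the step in both groups.

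**The case against.** - **The effect is bounded in time.** A reader might infer that the planned tables would show progressive worsening over years. They would not. Once nearly everyone is at 200 mg per day the artefact is complete, and visits run every 12 weeks for about 96 months (roughly 417 weeks, so about 34 visits). Only the reading across Weeks 12 to 36 is affected. This stands.
- **The size is not known.** No lower-dose means are given, and the dose-dependence statements come from CL-203; for CL-204 the protocol says only that laboratory data agreed with prior studies. About a third of core filgotinib subjects were already at 200 mg and have no planned step. US males and dose reductions make the Week 36 share less than 100%. This stands, and is why a range is shown.
- **The scope is limited.** A reader might extend the point to vital signs, which use the same clock (SAP 7.3). Protocol 6.5 reports no clinically relevant effect on vital signs, so nothing suggests a dose step there. Nor does it reach every laboratory test: Protocol 6.4 reports no lymphocyte decrease and describes testosterone as not dose-dependent.
- **Other outputs help.** The graded, liver and blood-count summaries (SAP 7.2.2 and 7.2.3) count worst or any post-baseline values, so week labels do not matter to them. The listings are chronological. No decision rests on the means: "No formal statistical testing is planned". This limits the harm but does not make the by-visit means readable.
- **The clock is a coherent choice.** It matches the definitions of exposure and of treatment-emergent events. That justifies keeping the planned tables, not leaving them as the only display.
- **The protocol already allows a split by mean actual dose (8.9.1.3).** It is optional and the SAP does not take it up. It would also separate poorly: 24 weeks at 50 mg and then 156 weeks at 200 mg average (24 × 50 + 156 × 200)/180 = 180 mg per day, close to the 200 mg of a subject who never stepped up.

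**Conclusion.** The point holds within limits. For neutrophils, platelets, creatinine and lipids, the by-visit means in SAP 7.2.1 confound dose with time over Weeks 12 to 36, mainly between Weeks 24 and 36. The change in dose mix over that last interval is large: from about 43% to near 100% at 200 mg per day in CL-203 and from about 50% to near 100% in CL-204, given equal roll-over by arm and leaving aside US males and dose reductions, whose numbers are not stated. The resulting shift in the mean could be small or substantial; the 14% to 74% range rests wholly on the assumed 25% to 75% effect at lower doses.

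The documents do not support a claim of distorted long-term trends after Week 36, or of a problem with vital signs. The matter is worth correcting because it touches the primary objective and needs no new data.

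**What to change.** Keep the planned tables. In SAP 7.2.1, for neutrophils, platelets, creatinine and lipids only, add a by-visit series indexed from CL-205 Day 1, using the Table 3-3 windows. Show the value and the change from the extension baseline (the definition in SAP 3.5.2, applied to these analytes), within each treatment group, by core-study daily dose at roll-over: placebo (CL-203 only), 50, 100 and 200 mg. Classify by dose at roll-over, because the 50 mg nonresponders had already moved to 100 mg at core Week 12. Subjects already at 200 mg have no planned step and serve as the internal reference: a shift seen only in the lower-dose rows points to the dose step, and a shift also seen in the 200 mg row points to time.

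Footnote the Table 3-5 outputs to say that Weeks 12 and 24 include doses below 200 mg per day.

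The cost is SAP wording and one further set of tables from data already held; entry values are the core Week 24 values (Protocol 8.7.1.1). The downside is more output and smaller cells by core dose. If the SAP is already final, SAP 1 provides for documenting the change in the CSR.

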7.2.2. Graded Laboratory Value

The CTCAE Version 4.03 will be used to assign toxicity grades to laboratory results for analysis. Grade 0 includes all values that do not meet the criteria for an abnormality of at least Grade 1. For laboratory tests with criteria for both increased and decreased levels, analyses for each direction (ie, increased, decreased) will be presented separately.

7.2.2.1. Treatment-Emergent Laboratory Abnormalities

Treatment-emergent laboratory abnormalities are defined as values that increase at least 1 toxicity grade from filgotinib baseline at any postbaseline time point, up to and including the date of last dose of filgotinib plus 30 days for subjects who permanently discontinued filgotinib in GLPG0634-CL-205, or the last available date in the database snapshot for subjects who were still on treatment at the time of an interim analysis.

If the relevant filgotinib baseline laboratory value is missing, any abnormality of at least Grade 1 observed within the time frame specified above will be considered treatment emergent.

7.2.2.2. Treatment-Emergent Marked Laboratory Abnormalities

Treatment-emergent marked laboratory abnormalities are defined as values that increase from filgotinib baseline by at least 3 toxicity grades at any postbaseline time point, up to and including the date of the last dose of filgotinib plus 30 days for subjects who permanently discontinued filgotinib in GLPG0634-CL-205 or the last available date in the database snapshot for subjects who were still on treatment at the time of an interim analysis.

If the relevant filgotinib baseline laboratory value is missing, any Grade 3 or higher values observed within the time frame specified above will be considered treatment-emergent marked abnormalities.

7.2.2.3. Summaries of Laboratory Abnormalities

Laboratory data that are categorical will be summarized using the number and percentage of subjects in the study with the given response at filgotinib baseline and each scheduled postbaseline visit.

The following summaries (number and percentage of subjects) for treatment-emergent laboratory abnormalities will be provided by lab test and treatment group; subjects will be categorized according to the most severe postbaseline abnormality grade for a given laboratory test:

- Graded laboratory abnormalities
- Grade 3 or higher laboratory abnormalities
- Marked laboratory abnormalities

For all summaries of laboratory abnormalities, the denominator is the number of subjects with nonmissing postbaseline values up to 30 days after last dosing date of filgotinib in GLPG0634-CL-205.

A by-subject listing of treatment-emergent Grade 3 or higher laboratory abnormalities and marked laboratory abnormalities will be provided separately by subject ID number and visit in chronological order. These listings will include all test results that were collected throughout the study for the laboratory test of interest, with all applicable severity grades or abnormal flags displayed.

